#### **4.3.1 Procedures for discontinuation of a subject from study treatment**

Any subject who discontinues study treatment for reasons other than disease progression should have tumour assessments performed as scheduled in the protocol (see Table 4) until disease progression is documented or death occurs, unless consent is withdrawn.

Patients may continue study treatment beyond disease progression if they are still receiving clinical benefit, as judged by the Investigator, and in the absence of any other discontinuation criteria.

### **4.4 Patient Withdrawal or Study Termination**

At any time, patients are free to discontinue AZD9291 treatment or withdraw from the study without prejudice to further treatment.

Reasons for withdrawal from the study:

- Eligibility criteria not fulfilled
- Death
- Withdrawal of consent.

If a subject wishes to withdraw their consent to both treatment and study assessments, they should be asked if they are willing to continue with survival follow-up (which can be conducted by telephone). If a subject wishes to withdraw their consent to further participation in the study entirely, including survival follow-up, this should be clearly documented in the subject notes and in the CRF.

The status of ongoing, withdrawn (from the study) and “lost to follow-up” subjects at the time of an overall survival analysis should be obtained by the site personnel by checking the subjects notes, hospital records, contacting the subjects general practitioner and checking publicly available death registries. In the event that the subject has actively withdrawn consent to the processing of their personal data, the vital status of the subject can be obtained by site personnel from publicly available resources where it is possible to do so under applicable local laws.

The withdrawal reasons must be documented and SAEs reported appropriately in the CRF. If the patient agrees, the investigator must follow the patient for safety reasons until 30 days post-last dose, and then for survival status (and also for progression status if the subject had not progressed). If patient declines, the investigator will separately follow up and manage any

SAEs as a matter of clinical practice. The patient or representative will return unused AZD9291 tablets.

AstraZeneca reserves the right to terminate the study. The study will be terminated if in the judgment of AstraZeneca, patients are placed at undue risk because of clinically significant findings or AZD9291 received national reimbursement.

The study will be closed in each participating country as soon as possible following national reimbursement of AZD9291 in that country (up to a max of 90 days post reimbursement). Enrolment will be closed within 6 months after market license approval in that country or at national reimbursement, whichever is sooner.

Patients withdrawing from the treatment prior to national reimbursement will be followed up as part of this study.

At national reimbursement, patients still on treatment will be transitioned to commercial supply as long as patient is benefitting from treatment as per investigator assessment and in accordance with national regulations in the countries where the study is conducted.. Once the study is closed no further data will be collected. Reasons for termination or withdrawal must be documented in the CRF. All data, collected as part of the study, that is available at the time of discontinuation from treatment, withdrawal from study or study termination, must be recorded.

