## **2. STUDY OBJECTIVE**

The primary objective of this study is to assess the efficacy and safety of single agent AZD9291 in a real world setting in adult patients with advanced or metastatic, epidermal growth factor receptor (EGFR) T790M mutation-positive Non-Small Cell Lung Cancer (NSCLC), who have received prior EGFR-tyrosine kinase inhibitor (TKI) therapy.

The primary efficacy outcome is OS, with secondary efficacy outcomes including investigator assessed response rate, investigator assessed PFS and Time to Treatment Discontinuation (TTD).

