- **Relevant Concomitant medication:** in case of SAE, AE of special interest, AE leading to dose modification (including study medication discontinuation).
- **AZD9291 dosing:** starting dose, dose adjustments, dose interruptions, dose discontinuation and reason for any dose change.
- **Disease assessment:** as per institutional standard of care, physicians will report in the CRF date, procedure, and best overall response at each follow-up visit time-point as well as if the patient is taking benefit from the study medication (yes/no). In case of disease progression, the physician will assess, date, and document in the CRF the progression and methods (eg CT scan) used as per standard definitions and routine institutional standard of care. Physician will also indicate if the patient progressed with leptomeningeal/brain metastasis.
  - Imaging assessments (CT scans or MRI) from baseline and following visits (where available and provided an Informed Consent is obtained) will be collected from a subset of patients where a T790M positive mutation was identified via the **cobas**® EGFR Mutation Test performed on a plasma or tissue specimen,
  - Imaging assessments (CT scans or MRI) from baseline and following visits (where available and provided an Informed Consent is obtained) may also be collected from patients where a T790M positive mutation was identified via other molecular testing methods.
- **Progression follow-up:** after study medication discontinuation for reasons other than disease progression, the patient will continue assessments as per institutional standard of care and the physicians will report in the CRF date, procedure, and best overall response at each follow-up visit.

- **Survival status:** patient survival status (dead, alive, unknown) at each follow-up must be documented in the CRF. The time from the date of first dose in the study until death will be used to evaluate OS. Lost to follow-up patients will be censored at last documented contact with patient status “alive”.
- **Laboratory assessments:** laboratory parameters will not be collected. If done, they will be assessed by the investigator as normal or abnormal and details about abnormality will be entered in the CRF.
- **Safety** will be assessed by collection of SAEs, AEs leading to dose-modification, AEs of special interest, and on-study deaths.

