## **9.2 Description of outcome variables in relation to objectives and hypotheses**

Analysis will be conducted to evaluate the following as available in the CRF:

- Baseline characteristics: demographics, relevant medical history, disease characteristics, cancer treatment history.
- Exposure to AZD9291
- Response Rate (RR):  
RR is defined as the percentage of patients with a best response of ‘responding’ by investigator assessment as recorded in the CRF.
- Overall Survival (OS):  
Overall survival is defined as the time from the date of first dose of AZD9291 in this study until death due to any cause. Any subject not known to have died at the time of analysis will be censored based on the last recorded date on which the subject was known to be alive.
- Progression Free Survival (PFS)  
PFS is defined as the time from first dose of AZD9291 in this study until the date of disease progression as recorded in CRF or death (by any cause in the absence of progression) regardless of whether the subject withdraws from therapy or receives another anti-cancer therapy prior to progression. Subjects who have not progressed or died at the time of analysis will be censored at the time of the latest date of assessment.
- Time to treatment discontinuation (TTD):  
TTD is defined as the time from the date of first dose of AZD9291 in this study until the date of AZD9291 discontinuation for any reason including disease progression, treatment toxicity, death or other reason as recorded in CRF. Subjects who are still on treatment at the time of analysis will be censored at the date of last dose received.
- Adverse events  
Serious Adverse Events [SAEs], adverse events leading to dose modification, and adverse events of special interest

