#### **9.4.1 Evaluation of primary efficacy objective**

OS will be summarized using Kaplan-Meier (KM) estimates of the median time to death or censoring and quartiles together with their 95% confidence intervals (CIs). KM estimates of the OS rate at appropriate time points (to be defined in SAP) will be presented as well. A plot of the KM overall survival curve will be produced.

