##### **3.1.1 Overall Survival (OS)**

The follow-up for the patients' survival status is to be performed every 6 weeks ( $\pm 1$  week) relative to the date of enrolment until end of study.

Overall survival is defined as the time from the date of first dose of AZD9291 in this study until the date of death due to any cause (i.e. date of death or censoring – date of first dose of AZD9291 in this study + 1). Any patient alive at study discontinuation will be censored at the study discontinuation date.

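### No single censoring rule covers patients searched for and not found dead, so OS can be biased downward where deaths are captured more completely than alive dates

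*Protocol*

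**What the plan says.** OS is the primary efficacy outcome (Protocol 2) and is summarised descriptively: "OS will be summarized using Kaplan-Meier (KM) estimates of the median time to death or censoring and quartiles" (Protocol 9.4.1).

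**Search.** Protocol 4.4 covers ongoing, withdrawn and lost patients. Site staff are to establish their status from patient notes and hospital records, and by "contacting the subjects general practitioner and checking publicly available death registries". For a patient who has withdrawn consent to data processing, only public sources may be used, where local law allows.

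**Censoring.** Three rules are given:
- Protocol 5: "Lost to follow-up patients will be censored at last documented contact with patient status" alive.
- Protocol 9.2: "Any subject not known to have died at the time of analysis will be censored based on the last recorded date" on which the patient was known to be alive.
- SAP 3.1.1: "Any patient alive at study discontinuation will be censored at the study discontinuation date".

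SAP 4.2.7, however, describes the censoring date of patients alive at their last assessment as the date last known alive. It counts prematurely censored patients and summarises their follow-up, but ties no sensitivity analysis to that count. SAP 6 records no change from the protocol. No section says how a patient who was searched for and not found dead is censored, or whether a death found after study discontinuation replaces an earlier censoring.

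**The concern.** A death registry returns deaths only. A lost patient who is found there becomes an event at the date of death, possibly long after last contact. A lost patient who is not found has had no new contact, so under Protocol 5 the censoring date does not move. Time after last contact then enters the risk set only for patients who died. Censoring depends on the outcome, and Kaplan-Meier is pulled down even if loss is unrelated to prognosis.

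This affects the median and the fixed-time OS rates of the primary outcome. The error does not shrink as N grows, so the narrow interval expected at N = 3500 would not reveal it. It can also differ between countries if registry access does.

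**Working it through.** **1. The plan's own figure.** Protocol 9.5 and SAP 1.3 assume exponential OS, a 58-month study and non-uniform accrual over 40 months. For N = 3500 and a 25-month median they give 1983 events and a 95% CI of 23.9-26.1. On the log scale, 25 × exp(±1.96/√1983) = 23.92 to 26.12, which agrees. The half-width is about 1.1 months. An entry distribution F(a) = (a/40)^2 returns the 1983 events and also the 2197 and 2085 events stated for medians of 21 and 23 months.

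**2. Why the asymmetry matters.** Define:
- λ = ln 2/25 = 0.0277 per month, and γ = the loss hazard, unrelated to prognosis
- pd = chance that a death after loss is found
- pa = chance that a lost patient still alive at closure gets an alive date there
- s = chance that a lost patient alive at t is still alive at closure
- U = exp(-(λ+γ)t), alive and not lost; L = exp(-λt)(1 - exp(-γt)), alive but lost

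Among patients whose potential follow-up exceeds t, the hazard that Kaplan-Meier estimates is

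λ × (U + pd·L) / (U + pd·L·(1 - s) + pa·L·s).

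If pd = pa the ratio is 1 and there is no bias. If pa = 0 the denominator lacks pd·L·s and the hazard is too high.

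Example: t = 24, γ = 0.006, pd = 0.9, pa = 0. L/U = exp(0.144) - 1 = 0.155. With the entry distribution above, s is about 0.75. The ratio is (1 + 0.139)/(1 + 0.035) = 1.10, so the hazard at month 24 is about 10% too high.

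**3. Size with uninformative loss and no alive dates recovered.** Simulation of 1,000,000 patients per scenario, true median 25. Loss hazards of 0.003, 0.006 and 0.012 per month give 5.9%, 11.3% and 20.9% lost. These and the search yields are assumptions.

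| Lost | 25% of later deaths found | 50% | 90% |
|---|---|---|---|
| 6% | 24.82 | 24.72 | 24.47 |
| 11% | 24.72 | 24.34 | 23.92 |
| 21% | 24.34 | 23.79 | 23.07 |

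The shifts are 25 - 24.82 = 0.18 to 25 - 24.47 = 0.53 month at 6% lost, and 0.28 to 1.08 months at 11% lost. A repeat run agreed to within about 0.1 month (24.0 in the 11%, 90% cell), so read the results to that accuracy. Censoring every lost patient at loss returns 25.0.

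**4. Alive dates recovered.** With 90% of deaths and 90% of living patients updated, the median is 25.0 at every loss rate. With 90% and 45%, it is 24.7, 24.5 and 24.0 at 6%, 11% and 21% lost, roughly half the shift.

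**5. Informative loss, 10% lost, no alive dates.** With half the deaths found and a post-loss hazard 2 or 3 times higher, the true medians are 23.7 and 23.1 and Kaplan-Meier gives 23.9 and 23.8: upward. With all deaths found it gives 23.4 against 23.9 and 22.9 against 23.2: still downward.

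**6. The SAP rule.** If study discontinuation is the patient's own exit and later deaths are ignored, the asymmetry goes, and with uninformative loss the median is 25.0. If it means study closure, patients not found dead are treated as alive to closure. With 10% lost and 20-50% of their deaths missed, the median is 25.3-26.2: upward.

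**The case against.** A reader might infer that the plan prescribes a one-sided rule and that OS is therefore certainly biased downward. The documents do not support that. Protocol 4.4 seeks status, not only deaths. Notes, hospital records and the general practitioner can all show a patient alive, and Protocol 9.2 would then move the censoring date forward. Protocol 4.1 also asks for every reasonable effort to establish the survival status of lost patients. The asymmetry remains only where no source returns an alive date. That is most likely in registry-only searches, including those for patients who withdrew consent to data processing.

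A reader might also infer that the SAP rule shares the asymmetry. Read literally, SAP 3.1.1 removes it, because a patient alive at discontinuation is censored there. What remains is that the term is not tied to one date, the treatment of later-found deaths is unstated, and the SAP differs from the protocol while reporting no change.

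It is fair to add that the study is single-arm and descriptive with no test, that survival is checked every 6 weeks, and that the SAP reports premature censoring. At 6% lost the shift lies inside the stated half-width of 1.1 months. These points lower the severity; they do not settle the rule.

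**Conclusion.** The point holds conditionally. The documents leave open a route by which deaths after last contact count while patients not found dead stay at their last alive date. Where deaths are captured more completely than alive dates and loss is not strongly related to prognosis, Kaplan-Meier OS is biased downward. For a 25-month median the shift is about 0.2 to 0.5 month at 6% lost and about 0.3 to 1 month at 11% lost, the latter approaching the plan's own half-width at N = 3500. These sizes assume uninformative loss and no recovered alive dates; neither the loss rate nor the search yield is in the documents.

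The direction is not fixed: equal capture under uninformative loss removes the bias, and strongly informative loss with incomplete registries makes it upward. It would also be wrong to conclude that registry-only deaths should leave the primary analysis. At 11% lost with a doubled post-loss hazard, dropping all post-loss deaths gives 25.0 against a true 23.7. This should be fixed, but it does not invalidate the plan.

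**What to change.** In Protocol 4.4, 5 and 9.2 and SAP 3.1.1, adopt one rule before the OS analysis:

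1. Set a common survival cut-off for each analysis, or country closure if earlier, and define study discontinuation against it.
2. Record the source and date of every status check, and record alive findings as completely as deaths.
3. Where a registry is complete enough that a negative search means alive, censor at its coverage date (or the cut-off if earlier) and count deaths only up to that same date. With 98% of deaths found, this stays within about 0.1 month of the truth at the loss rates and post-loss hazards tried.
4. Elsewhere, keep found deaths in the primary analysis. Add a sensitivity analysis that censors lost or withdrawn patients at last direct alive contact and ignores deaths found only by later search.

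The cost is revised wording, one extra data field and one extra analysis.

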## 5. STUDY MEASURES

The sources of information for all study variables collected for this study will be patient medical records or charts and patients surveys. All data collected will be entered by the investigator into a CRF. All patients participating in the study will be followed from enrolment until completion of the study, discontinuation of AZD9291 administration (determined by investigator due to adverse events, toxicities or other relevant reasons), discontinuation due to disease progression, or death, whichever occurs earlier.

Study measures will be collected at baseline and during the follow-up period. For each patient, physicians will be required to provide date of enrolment, and thereafter during the follow-up visits, the date and outcome of the more recent disease assessment, and date of progression and death (if applicable). The variables described in the following sections will be collected to address the study objectives.

The study measures that will be assessed among patients participating in this study are listed below:

- **Baseline demographic characteristics:** patient characteristics including age, gender, race (if available or allowed by local regulations) will be collected
- **T790M** positive mutation status results and type of test performed and receptors

- **Relevant Medical history:** comorbidities and relevant medical history (this includes any chronic conditions currently requiring medication)
- **Physical examination:** at baseline and at treatment discontinuation
- **Weight:** at each visit
- **Visual test:** at screening, a slit-lamp examination should be obtained. Ophthalmologic exams to be performed as clinically indicated. A 30-day follow-up assessment will be required if an on treatment assessment was abnormal at the time of discontinuation of study therapy, to confirm reversibility of the abnormality.
- **Disease characteristics:** tumor histology, stage at diagnosis, current stage, presence of leptomeningeal /brain metastases at baseline, WHO performance status at study enrollment and subsequent follow-up visits
- **Cancer treatment history:** first-line therapy type (targeted or non-targeted) and agents received, start and end-dates, subsequent-lines type and start and end-date, radiation therapy (yes/no), surgery (yes/no) received prior to study enrollment must be documented
- **Relevant Concomitant medication:** in case of SAE, AE of special interest, AE leading to dose modification (including study medication discontinuation).
- **AZD9291 dosing:** starting dose, dose adjustments, dose interruptions, dose discontinuation and reason for any dose change.
- **Disease assessment:** as per institutional standard of care, physicians will report in the CRF date, procedure, and best overall response at each follow-up visit time-point as well as if the patient is taking benefit from the study medication (yes/no). In case of disease progression, the physician will assess, date, and document in the CRF the progression and methods (eg CT scan) used as per standard definitions and routine institutional standard of care. Physician will also indicate if the patient progressed with leptomeningeal/brain metastasis.
  - Imaging assessments (CT scans or MRI) from baseline and following visits (where available and provided an Informed Consent is obtained) will be collected from a subset of patients where a T790M positive mutation was identified via the **cobas**® EGFR Mutation Test performed on a plasma or tissue specimen,
  - Imaging assessments (CT scans or MRI) from baseline and following visits (where available and provided an Informed Consent is obtained) may also be collected from patients where a T790M positive mutation was identified via other molecular testing methods.
- **Progression follow-up:** after study medication discontinuation for reasons other than disease progression, the patient will continue assessments as per institutional standard of care and the physicians will report in the CRF date, procedure, and best overall response at each follow-up visit.

- **Survival status:** patient survival status (dead, alive, unknown) at each follow-up must be documented in the CRF. The time from the date of first dose in the study until death will be used to evaluate OS. Lost to follow-up patients will be censored at last documented contact with patient status “alive”.
- **Laboratory assessments:** laboratory parameters will not be collected. If done, they will be assessed by the investigator as normal or abnormal and details about abnormality will be entered in the CRF.
- **Safety** will be assessed by collection of SAEs, AEs leading to dose-modification, AEs of special interest, and on-study deaths.

### **Central reading of imaging assessments**

All imaging assessments from a selected subset of patients (where available and Informed Consent is obtained), including unscheduled visit scans, should be collected and sent to an AstraZeneca appointed Clinical Research Organisation to enable independent central analyses. The central imaging review is required only for this selected subset of patients where a selected T790M positive mutation test was performed on a plasma or tissue specimen. The baseline scan should ideally be performed within 28 days of the start of treatment. The results of this independent review will not be communicated to investigators. The purpose of this review is to assess tumour response according to RECIST 1.1 in order to evaluate the objective response rate in these subsets of patients with various methods of T790M molecular testing.

Further details will be provided in the Statistical Analysis Plan.

## **6. SAFETY REPORTING AND MEDICAL MANAGEMENT**

The investigator is responsible for reporting all serious adverse events and the other adverse events specifically defined on [Table 4](#) and ensuring that all staff involved in the study is familiar with the content of this section.

### **6.1 Definition of adverse events**

An AE is the development of an undesirable medical condition or the deterioration of a pre-existing medical condition occurring at any time from signing informed consent, whether or not considered causally related to the investigational drug. An undesirable medical condition can be symptoms (e.g., nausea, chest pain), signs (e.g., tachycardia, enlarged liver) or the abnormal results of an investigation (e.g., laboratory findings, electrocardiogram).

